6.3.5. Optional Liver Biopsy Substudy

One optional liver biopsy can be performed (in participants who consent to do so and as per investigator’s judgement) during Year 1 postinfusion and/or subsequently during Years 2-5 postinfusion. The procedure may be repeated once, later in the study, to assess evolution over time (in participants who consent to do so and as per investigator’s judgement).

This substudy may be proposed to any participant, unless there is a condition that, in the opinion of the investigator or a hepatologist or radiologist, would make liver biopsy contraindicated.

The exploratory objectives of the substudy are to evaluate vector integration in the liver, the histopathology of the liver tissue and to assess the expression of protein and/or RNA levels of FVIII and other biomarkers of interest in the liver (depending on collected material). A biopsy will be made upon investigator’s decision; it can be performed at any time to assess liver health, integration and FVIII in the liver, but could also be triggered by sustained elevated FVIII activity levels, by a significant FVIII activity decline, by a sustained ALT elevation $>$ ULN or to assess the long-term gene therapy effects on the liver.

Liver biopsy will be performed on few participants only and most probably at different timepoints for each participant, so mainly a description of the findings for each biopsy will be provided.

6.4. Subset Analyses

Not applicable.

6.5. Baseline and Other Summaries and Analyses

6.5.1. Baseline Summaries

Demographic information, baseline characteristics of ‘Dosed’ population will be summarized. Medical history/Hemophilia history data at study entry, including information collected in the lead-in study (C0371004) will also be summarized.

In addition, demographic and baseline characteristics will be summarized separately for the main analysis population (i.e., ‘Efficacy’ population).

6.5.2. Study Conduct and Participant Disposition

The participants’ disposition will be summarized.

6.5.3. Study Treatment Exposure

Since there is only one dose of the study medicine, there is no plan to measure treatment exposure or compliance in this study. Instead, the percentage of participants with partial dose of PF-07055480 infusion will be reported.

6.5.4. Concomitant Medications and Nondrug Treatments

Concomitant medication other than FVIII replacement infusions, which will be summarized separately as a secondary endpoint, and non-drug treatment will be summarized.

The following data will be summarized to assess corticosteroid treatment:

- Participants (%) with corticosteroid treatment.
- Participants (%) with corticosteroid dose escalation during corticosteroid treatment. In addition, number (%) of participants by number of dose escalations will be reported.
- Time to corticosteroid initiation: to be calculated as [date of first corticosteroid initiation – girooctocogene fitelparvovec infusion date +1].
- Total time on corticosteroids: to be calculated as [stop date of last dose of corticosteroid – date of initiation of first dose of corticosteroid +1] excluding days without corticosteroid use during the period from first corticosteroid initiation until the last dose of corticosteroid.
- The entire duration from corticosteroid initiation through the last administration: to be calculated as [last date of corticosteroid treatment – first date of corticosteroid initiation + 1].
- Duration of follow-up (in days) post cessation of the latest corticosteroid therapy in the participants who received corticosteroid: to be calculated as [data cut-off date or discontinuation date (whichever comes earlier) – stop date from the last dose of corticosteroid]. Days of follow-up duration will be converted to months.
- Cumulative prednisone-equivalent dose. Both dose and frequency will be included for the calculation of cumulative dose. Doses of different corticosteroid concomitant medications will be converted to prednisone-equivalent dose using the following conversion table. For example, one dose of triamcinolone is equal to $5/4=1.25$ prednisone-equivalent dose. The prednisone-equivalent dose for budesonide is $5/1.125=4.44$.

Glucocorticoids	Equivalent dose (mg)
Short-acting	
Cortisol	
Cortisone	20
Intermediate-acting	
Prednisone	25
Prednisolone	5
Triamcinolone	4
Methylprednisolone	4
Budesonide	1.125
Long-acting	
Dexamethasone	0.75
Betamethasone	0.6
Mineralocorticoids	
Fludrocortisone	2
Sources provided in Section 8 .	

- Average daily prednisone-equivalent dose per participant.
- Number of corticosteroid courses per participant. A corticosteroid course will be defined below per participant and used to calculate number of CS (corticosteroid) courses: The start date of a CS course will be defined as the time of the first dose of CS or when a dose increase was made. The end date will be defined as the day before CS use was discontinued, or the day before a dose increase was made.

FVIII replacement infusion post PF-07055480 infusion will be reported in a separate data listing in addition to summary tables as described in [Section 6.2.3](#) and [Section 6.2.6](#).

6.6. Safety Summaries and Analyses

All safety analyses, including analyses of AEs, clinical laboratory results, vital signs, and physical examinations will be conducted on the ‘Safety’ analysis population. In this study, ‘Safety’ population is the same as ‘Dosed’ population.

6.6.1. Adverse Events

The AE data will be summarized following the latest available version of MedDRA.

An overall table summarizing TEAEs reported during the entire study will be sorted by System Organ Class (SOC) and Preferred Term (PT). Per protocol, adverse events assessed as non-serious and unrelated to study drug are reported within the first two years postinfusion only and are not subject to reporting thereafter. Therefore, the all causality TEAE tables will include a footnote to convey non-serious unrelated AEs were collected over the first two years and not the subsequent 3-year study duration for a given participant.

All TEAEs occurring during the short-term monitoring period (up to and including 104 weeks postinfusion) will be summarized, sorted by SOC and PT. All AE summary tables

will be generated to display all AEs, relationship to study drug, and severity of the AEs ('Mild', 'Moderate', and 'Severe').

All serious AEs, treatment-related non-serious AEs, events of special interest, AEs related to corticosteroid treatment as deemed by the investigator, AEs leading to study discontinuation, and AEs leading to death will be summarized for adverse events reported during the short-term monitoring period (up to and including 104 weeks postinfusion) and AEs reported during the long-term monitoring (Week 105 post PF-07055480 infusion up to EOS), respectively if data are available.

TEAEs and SAEs will be summarized separately for the 'Safety' population.

6.6.2. Laboratory Data

Data of safety laboratory tests and other laboratory tests collected at scheduled study visits will be summarized according to the data type. Data collected at both scheduled visit and unscheduled visits will be included in plots.

Any important laboratory abnormality identified will be summarized as described below.

Categorical shift of abnormal to normal, or normal to abnormal, in liver function test (LFT), α -Fetoprotein (AFP), hematology, and clinical chemistry parameters will be summarized.

Laboratory tests included in LFT measures are listed in the Protocol Appendix 2. Baseline and post baseline observations will be summarized with descriptive statistics by visit and will be presented in a data listing. Number of participants (n), mean, SD, median, Q1, Q3, min and max will be presented for all change from baseline tables. Individual laboratory values will be classified according to whether the test result is 'low' (i.e., below the lower limit of normal), 'normal' (i.e., within the normal range), or 'high' (i.e., above the upper limit of normal). The abnormality categorical data will be summarized in shift tables comparing the results at the end of study visit, minimum post-baseline, and maximum post-baseline with those at the baseline visit.

The following laboratory tests presented in [Table 9](#) will be reported in shift tables.

Table 9. Laboratory Tests to be Presented in Shift Tables

Hemoglobin
Hematocrit
Selected LFTs, including albumin, alanine transaminase (ALT), aspartate transaminase (AST), bilirubin (total, direct), alkaline phosphatase (ALP), gamma-glutamyl transferase (GGT), lactic acid dehydrogenase (LDH)
AFP
aPTT (in ratio), INR, TAT, TGA, D-dimer
White blood cell (WBC) count total
Neutrophils
Lymphocytes
Monocytes
Eosinophils
Basophils
Serum creatinine

An individual participant plot that presents ALT/AST, factor activity levels, ELISPOT data, corticosteroid use and dose, bleeding episodes and factor replacement infusions will be provided for each participant in the ‘Safety’ population. Three panels will be provided for each individual plot. In the top panel, FVIII activity (based on central chromogenic assay) and ALT/AST levels over time will be plotted, with all bleeds and exogenous FVIII infusions marked. ELISPOT data (selected parameters related to T-cell response to AAV capsid protein and FVIII) over time will be plotted underneath as a separate panel. The start/stop days of corticosteroid with corresponding doses will be plotted in the last panel.

In a case when a FVIII infusion has to be administered for a planned surgery or resumption of prophylaxis regimen, the FVIII activity data collected by local labs before FVIII infusion and 30 minutes post FVIII infusion will be used to calculate the recovery as [(FVIII activity post FVIII infusion – FVIII activity pre FVIII infusion)/dose of FVIII infusion]. This calculated recovery will be compared to the expected recovery in hemophilia A population, based on the number of units infused. A data listing will be provided with participant-level data of FVIII activity levels (pre and post FVIII infusion), dose of FVIII infusion, and calculated recovery.

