If corticosteroid therapy is started, measurement of LFTs and of FVIII activity is recommended at least 2 times per week until the end of this therapy.

The following schedule of combined oral corticosteroids and intravenous corticosteroids (methylprednisolone) is recommended if there is no evidence of resolution of transaminase elevation or persistent loss of FVIII activity while on oral corticosteroids treatment alone ([Table 2](#)).

Table 2. Recommended Regimen for Combination Intravenous and Oral Corticosteroids

Schedule (corticosteroid treatment regimen)	Oral Prednisolone/Prednisone (mg/day)	Intravenous Methylprednisolone (g/day)
Days 1 to 3	n/a	1
Days 4 to 7	20	n/a
Week 2	60	n/a
Week 3	60	n/a
Week 4	40	n/a
Week 5	30	n/a
Week 6	30	n/a
Week 7	20	n/a
Week 8	10	n/a
Week 9	5	n/a

The investigator will have flexibility in implementing the immunomodulatory regimen because the exact regimen and course will depend on clinical circumstances. If the investigator chooses an immunosuppressive regimen that differs from that suggested above, the investigator should discuss the plan with the Sponsor's medical monitor; this discussion should not delay initiation of immunosuppression.

The long-term side effects of the immunomodulatory drugs to be considered in this study are well characterized. Participants who develop immune hepatitis will be monitored closely to minimize the risk of the side effects. To use the lowest effective dose and to shorten the duration of the immunosuppressive therapies, tapering of the regimen will start as soon as there is evidence of resolution of hepatic transaminases elevation and FVIII activity has plateaued. If available, ELISPOT results will be monitored during tapering. While on immunomodulatory regimens, participants will also be monitored for side effects, such as opportunistic infections. Antibiotics or other medications to minimize the risk of opportunistic infection may be prescribed at the discretion of the investigator. All events related to the use of immunomodulatory drugs (eg, hyperglycemia, weight gain, infections) will be recorded as AEs connected to their use.

- If 2 or more participants are nonresponsive to immunomodulatory regimens, or if the value of the transaminases continues to rise, the Sponsor's medical monitor and investigator will discuss more intensive immunomodulatory regimens. The Sponsor will convey the information to the eDMC.

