6.6.4. Immunogenicity

Percentage of participants with positive/negative interferon gamma (IFN γ) to each AAV or FVIII pool, FVIII overall and capsid overall, compare to baseline, will be summarized by the specified sampling timepoint for participants in whom the corticosteroid treatment is initiated.

Descriptive summaries will be provided for nAb to AAV titer by study visit. Number and percentage of participants with positive nAb to AAV will be summarized by study visit. Unscheduled assessments will also be presented. Data will also be presented in a listing.

Descriptive summaries will be provided for ADA by study visit. Number and percentage of participants with positive ADA will also be summarized by study week. Unscheduled assessments will also be presented. Data will also be presented in a listing.

One line plot will be generated, plotting FVIII activity level at Week 52 based on central chromogenic assay against ADA titer at Screening visit and ADA titer at Week 52, respectively.

Number and percentage of participants with FVIII inhibitor by the Bethesda Assay will be summarized by study visit.

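### As worded, the SAP builds its worst-value liver shift tables from scheduled samples only, so an ALT, AST or bilirubin abnormality seen only on an unscheduled draw would be tabulated as normal

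*SAP*

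**What the plan says.** SAP 6.6.2 (Laboratory Data) opens with the rule for tables: "Data of safety laboratory tests and other laboratory tests collected at scheduled study visits will be summarized according to the data type". The next sentence covers figures: "Data collected at both scheduled visit and unscheduled visits will be included in plots". Further down, values are classed as low, normal or high and presented in "shift tables comparing the results at the end of study visit, minimum post-baseline, and maximum post-baseline with those at the baseline visit". SAP Table 9 lists the tests concerned, including ALT, AST, and total and direct bilirubin. The shift sentence names no data source and makes no exception for unscheduled samples.

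Elsewhere the SAP mentions unscheduled data when it wants them. Section 3.2.1 includes them in the Week 65 FVIII activity value. Section 6.6.4 says of the antibody results: "Unscheduled assessments will also be presented".

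The protocol expects unscheduled liver tests. Section 8.2.6 asks for clinically significant abnormal results to be repeated until they settle. Section 8.3.10 says that, once corticosteroids are started, "measurement of LFTs and of FVIII activity is recommended at least 2 times per week until the end of this therapy". Appendix 6 calls for repeat testing in suspected Hy's law cases. The Schedule of Activities (1.3) has liver tests, including unscheduled and repeat ones, run at both local and central laboratories.

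**The concern.** A maximum post-baseline table is meant to show the worst value each participant had. In this trial the extra samples are drawn mainly because something looks abnormal. A rule that keeps only scheduled samples therefore drops the samples most likely to hold the extreme.

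Hepatotoxicity is the first of the main potential risks in the protocol synopsis, and laboratory tests are a stated safety endpoint (SAP 3.5). If the only out-of-range value for a test lies on an unscheduled draw, the participant is counted as normal-to-normal for that test. Bilirubin is the clearest case. Protocol Appendix 6 notes that transaminase rises usually precede bilirubin rises by days or weeks. A late scheduled draw could therefore show raised ALT with normal bilirubin, and the bilirubin rise could appear only on repeat testing. The individual participant plot in SAP 6.6.2 shows ALT and AST but not bilirubin, so it would not fill that gap.

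**Working it through.** The plan gives no figure on this point to reproduce. The check has three parts.

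**1. Which samples feed the maximum.** The opening rule sends scheduled data to summaries and sends scheduled plus unscheduled data to plots. The shift tables are summaries in the same section with no rule of their own. The SAP names unscheduled data explicitly for FVIII activity and antibodies. The natural reading is scheduled-only, but it is an inference from the opening sentence.

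**2. How many liver test draws are scheduled.** Minimum post-infusion draws from the Schedule of Activities:

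- Weeks 1-12, at least 2 per week: 12 × 2 = 24
- Weeks 13-20, 2 per week: 8 × 2 = 16
- Weeks 22, 24, 26, 28, 30, 32, 34: 7
- Weeks 38, 42, 48, 52: 4
- Weeks 65, 78, 91, 104, 117, 130, 143, 156: 8
- Weeks 182, 208, 234, 260: 4

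Total: 24 + 16 + 7 + 4 + 8 + 4 = 63.

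Take a corticosteroid course of 8 weeks, the basic length in protocol Table 1, sampled twice weekly: 8 × 2 = 16 draws. Count the scheduled weeks falling inside the 8-week window, ignoring visit windows:

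| Course timing | Scheduled, of 16 | Unscheduled share |
|---|---|---|
| Wholly within Weeks 1-20 | 16 | 0/16 = 0% |
| Starts Week 22 or 26 | 4 | 12/16 = 75% |
| Starts Week 34 or 38 | 2 | 14/16 = 88% |
| Starts Week 52 | 1 | 15/16 = 94% |
| Starts Week 66, 80 or 157 | 0 | 16/16 = 100% |

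The first row depends on counting laboratory-only draws as scheduled study visits, which the SAP does not settle. If the term means numbered visits, there are 15 after infusion. Only six of them (Weeks 1, 2, 4, 8, 12, 18) fall by Week 20, against 24 + 16 = 40 scheduled draws. The window of about 3 to 10 weeks in which protocol 2.3.1 expects liver effects would then rest on Weeks 4 and 8.

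**3. From samples to table categories.** Adding samples can only raise a maximum or lower a minimum, so omitting them can only understate abnormality. But the categories are low, normal and high, with no multiples of the upper limit of normal. An omitted high value changes a participant's entry only if no scheduled post-infusion value of that test was high, and likewise for low. The documents give no rate for that event, so no number of misclassified participants can be calculated.

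**The case against.** The strongest reply is that the restriction is not written into the shift sentence. The abnormality tables follow a separate lead-in about important abnormalities, and that text refers to individual values and to post-baseline extremes without limiting the visits. The sponsor may already intend to use all samples. That is possible. But the only source rule in the section points the other way, and two programmers could produce different tables from the same text.

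A reader might infer from the table of shares that most late liver abnormalities, or most ALT peaks, will be lost. The documents do not support that. The shares count samples. Where a scheduled draw found the raised ALT that prompted treatment, the participant is already classed as high and repeats cannot alter that. Peak height is not shown in these shift tables whatever the data source.

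A reader might also infer that the main period of risk is affected. If laboratory-only draws count as scheduled, it is not: scheduled sampling through Week 20 already matches the twice-weekly rate recommended during corticosteroids.

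Nor would serious events go unreported. Potential Hy's law cases are SAEs (Appendix 6), as are drug-related transaminase rises that do not respond to immunosuppression (10.3.2). Laboratory abnormalities needing further testing or intervention are AEs (10.3.1), although after Week 104 non-serious AEs are collected only if related or of unknown causality (8.3.1). Unscheduled ALT and AST values appear in plots, and corticosteroid use is tabulated. These routes limit the harm. They do not correct a shift table that reads normal-to-normal.

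**Conclusion.** The point stands in a limited form. On the plain reading of SAP 6.6.2, the minimum and maximum post-baseline shifts omit unscheduled samples. A participant whose only out-of-range ALT, AST or bilirubin value is on such a sample would be shown as normal throughout for that test. The bias runs one way. It falls mainly after Week 20, provided laboratory-only draws count as scheduled; if they do not, the early weeks are affected too. Its size in participants cannot be derived from the documents, and the shares of 0%, 75%, 88% and at least 94% should not be read as misclassification rates. They assume an 8-week course at the recommended minimum of two draws per week.

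This concerns a descriptive safety table. No efficacy result or type I error is touched. It should still be corrected, because liver safety is central to this product and the wording leaves the table open to two constructions.

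**What to change.** In SAP 6.6.2, state three things:

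- Minimum and maximum post-baseline values in the Table 9 shift tables use all post-infusion central-laboratory results, scheduled and unscheduled.
- Results available only from a local laboratory are either classified against that laboratory's own normal range or listed separately, so that one maximum does not mix sources.
- Laboratory-only draws in the Schedule of Activities count as scheduled.

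Keep the by-visit descriptive summaries on scheduled samples.

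The cost is a few sentences and slightly more programming, with no new data collection. More participants may appear as shifting to abnormal. The maximum will also depend partly on how often a participant was sampled, which a footnote can say. If all samples were always intended, the change simply records it.

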6.6.3. Vital Signs/ Physical Examination/Other Safety Outcome

Vital signs by visit, electrocardiograms, liver ultrasounds, and abnormal findings from physical examination will be summarized according to the data type.

6.6.4. Immunogenicity

Percentage of participants with positive/negative interferon gamma (IFN γ) to each AAV or FVIII pool, FVIII overall and capsid overall, compare to baseline, will be summarized by the specified sampling timepoint for participants in whom the corticosteroid treatment is initiated.

Descriptive summaries will be provided for nAb to AAV titer by study visit. Number and percentage of participants with positive nAb to AAV will be summarized by study visit. Unscheduled assessments will also be presented. Data will also be presented in a listing.

Descriptive summaries will be provided for ADA by study visit. Number and percentage of participants with positive ADA will also be summarized by study week. Unscheduled assessments will also be presented. Data will also be presented in a listing.

One line plot will be generated, plotting FVIII activity level at Week 52 based on central chromogenic assay against ADA titer at Screening visit and ADA titer at Week 52, respectively.

Number and percentage of participants with FVIII inhibitor by the Bethesda Assay will be summarized by study visit.

